8.1.5.2 Dose Withheld

NM21-1480 will be withheld for any of the following treatment-emergent adverse events (TEAEs):

- Any Grade ≥ 2 TRAE, with the following exceptions:
 - Grade 2 TRAE fatigue, alopecia, skin rash or laboratory abnormalities do not require a treatment delay
- Any Grade 3 skin, TRAE
- Any Grade 3 TRAE laboratory abnormality, with the following exceptions for lymphopenia, AST, ALT, or total bilirubin or asymptomatic amylase or lipase:

- Grade 3 lymphopenia does not require dose delay
- If a patient has a baseline AST, ALT or total bilirubin that is within normal limits, delay dosing for treatment-related Grade ≥ 2 toxicity
- If a patient has baseline AST, ALT, or total bilirubin within the Grade 1 toxicity range, delay dosing for treatment-related Grade ≥ 3 toxicity
- Any Grade ≥ 3 treatment-related amylase or lipase abnormality that is not associated with symptoms or clinical manifestations of pancreatitis does not require dose delay. The Medical Monitor should be consulted for such Grade ≥ 3 amylase or lipase abnormalities
- Any AE, laboratory abnormality, or intercurrent illness which, in the judgement of the Investigator, warrants delaying the dose of study medication.
- Grade 2 TRAEs that recur shall be managed by dose modifications (changes in the infusion rate) and dose delays, and those that do not resolve to Grade 1 or less by the end of the next treatment cycle shall lead to permanent discontinuation of NM21-1480. Pre-planned dose level reductions are not allowed; however, interruptions in delivering the planned dose that results in an actual dose that is less than 90% of the planned dose is defined as dose reduction.

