8.1.7 Management of Infusion-Related Reactions

Infusion-related reactions may occur during or after administration of NM21-1480. Dose reductions, other than a decrease in the infusion rate, are not allowed. Management guidelines for infusion reactions are displayed in [Table 8-1](#).

Table 8-1 Management of Infusion-related Reactions

NCI CTCAE Grade	Treatment	Premedication at Subsequent Dosing
Grade 1 Mild reaction; infusion interruption not indicated; intervention not indicated	
Increase monitoring of vital signs as medically indicated until the symptoms have resolved.
 
The infusion rate of study drug/study regimen may be decreased by 50% or temporarily interrupted until resolution of the event.
	
Patient may be pre-medicated at the discretion of the Investigator as per institutional norm or consider premedication 1.5 hours (\pm 30 minutes) prior to infusion of NM21-1480 with:
 
• Diphenhydramine 50 mg orally (or equivalent dose of antihistamine)• Acetaminophen (Paracetamol) 500-1000 mg orally (or equivalent dose of antipyretic)
Grade 2 Requires infusion interruption but responds promptly to symptomatic treatment (e.g., antihistamines, NSAIDs, narcotics, IV fluids); prophylactic medications indicated for \leq 24 hours	
Stop infusion and monitor symptoms.
 
Additional appropriate medical therapy may include but is not limited to: IV fluids, antihistamines, NSAIDs, acetaminophen, and narcotics.
 
Increase monitoring of vital signs as medically indicated until the symptoms have resolved.
 
If symptoms resolve within 1 hour of stopping IP infusion, the infusion may be restarted at 50% of the original infusion rate (e.g., from 100 to 50 mL/hour). Otherwise, dosing will be held until symptoms resolve and the participant should be pre-medicated for the next scheduled dose.
 
Participants who develop Grade 2 toxicity despite adequate premedication should be permanently discontinued from further IP administration.
	
Patient should be pre-medicated as per institutional norm or consider premedication 1.5 hours (\pm 30 minutes) prior to infusion of NM21-1480 with:
 
• Diphenhydramine 50 mg orally (or equivalent dose of antihistamine)• Acetaminophen (Paracetamol) 500-1000 mg orally (or equivalent dose of antipyretic)

NCI CTCAE Grade	Treatment	Premedication at Subsequent Dosing

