9.2.4.3 Action Taken with Study Drug Due to AE

The action taken with study drug should be recorded using one of the following:

- None
- Study drug temporarily discontinued
- Study drug permanently discontinued
- Unknown/not applicable

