9.2.4.4 Other Action Taken

Details of any other actions taken should be specified:

- Specific therapy/medication
- Surgical medical procedure
- Prolonged hospitalization

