10.6.6 Adverse Events

Adverse events will be coded using the most current version of the MedDRA. Incidence tables will be presented for all AEs by maximum grade according to CTCAE v5.0. Adverse events, SAEs, TEAEs, TRAEs (i.e., assessed as at least possibly related to study drug by the Investigator), and AEs resulting in dose reduction, interruption, or discontinuation of study drug will be tabulated, as well as AEs leading to additional therapy. Dose-limiting toxicity will also be tabulated. Summaries for deaths on study will be provided by system organ class and preferred term. Adverse event of special interest for NM21-1480 will be identified according to the most recent case retrieval strategy prior to database lock. Such categories consist of 1 or more well defined safety events which are similar in nature and for which there is a specific clinical interest in connection with the study treatment. For each specific category, number and percentage of patients with at least 1 event will be reported. Additional analyses (including time to onset and duration) may also be performed for these events.

Adverse event of special interest do not require expedited reporting to the Sponsor unless the event(s) meets SAE reporting criteria ([Section 9.2.6](#)).

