3.6.2 Adverse Events (AEs)

AEs will be captured from signing informed consent/HIPAA authorization, through 70 days after the last dose of study drug, as specified in section 9.2.4 of the protocol. Beyond 70 days from the last dose of study drug, only study treatment-related SAEs or late-occurring irAEs should be reported. All AEs will be coded to system organ class and preferred term using MedDRA version 25.0 or later.

Treatment-emergent adverse events (TEAEs) are defined as AEs that occur or worsen on or after the first dose of study drug.

Adverse events of special interest (AESIs) are defined in section 9.2.1.6 of the protocol as:

- Elevations of ALT/AST that are >3-fold above baseline,
- AEs falling under the system order class (SOC) of hepatobiliary disorders (i.e., to cover any potential liver toxicity) Grade 3 or higher,
- SOC of immune system disorders (i.e., to cover cytokine release syndrome and irAEs) Grade 3 or higher,
- Any AE of CTCAE V5.0 Grade 3 or higher,
- Any CTCAE V5.0 Grade 3 or 4 infusion reaction whether or not the event is a DLT or delayed DLT,
- Any AE considered by the Investigator to represent a DLT or delayed DLT.

AESI's will be identified by the investigator and recorded in the eCRF.

Immune-related AEs (irAEs) will be identified by the investigator and recorded in the eCRF.

An overview of AEs will be provided including counts and percentages of subjects (and event counts) with the following types of AEs:

- Any TEAEs (overall, by maximum severity, and grade ≥ 3)
- Any NM21-1480-related TEAEs (overall, by maximum severity, and and grade ≥ 3)
- Any TEAEs of special interest (overall, by maximum severity, and grade ≥ 3)
- Treatment-emergent irAEs
- Any serious AEs (SAEs)
- Any treatment-emergent serious AEs (TESAEs)
- Any NM21-1480-related TESAEs
- Any TEAEs leading to temporary or permanent discontinuation of NM21-1480
- Any AEs leading to death

The number and percentage of patients with AEs will be summarized by system organ class (SOC) and preferred term (PT) for the following types of AEs:

- TEAEs
- Grade ≥ 3 TEAEs

- NM21-1480-related TEAEs
- Grade ≥ 3 NM21-1480-related TEAEs
- TEAEs of special interest
- Treatment-emergent irAEs
- TESAEs
- NM21-1480-related TESAEs

The number and percentage of patients with AEs will be summarized by SOC, PT, and highest CTCAE grade for the following types of AEs:

- TEAEs
- NM21-1480-related TEAEs

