All adverse event data will be listed by patient. Additional listings will present SAEs, AESIs, irAEs, TEAEs leading to temporary or permanent discontinuation of NM21-1480, TEAEs leading to discontinuation of study, and AEs leading to death.

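### The SAP's adverse event overview pools temporary holds with permanent stops of NM21-1480, and two tabulations promised in protocol 10.6.6 are missing without being declared

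*SAP*

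**What the plan says.** SAP 3.6.2 (Adverse Events) lists the rows of the overview table. One of them is "Any TEAEs leading to temporary or permanent discontinuation of NM21-1480". No breakdown is given for it. The listings planned at the end of the same section use the same combined category: "TEAEs leading to temporary or permanent discontinuation of NM21-1480, TEAEs leading to discontinuation of study", followed by deaths.

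Protocol 10.6.6 (Adverse Events) sets out what was promised: "AEs resulting in dose reduction, interruption, or discontinuation of study drug will be tabulated, as well as AEs leading to additional therapy".

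Protocol 9.2.4.3 has the action taken with study drug recorded in one of four categories. Temporary discontinuation is one, and "Study drug permanently discontinued" is another. Protocol 9.2.4.4 records other actions, including "Specific therapy/medication".

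SAP section 6 (Changes from protocol-specified statistical analysis) gives the low enrolment as the reason for producing a reduced set of outputs and no interim analysis. It names no adverse event summary.

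**The concern.** Safety and tolerability is a primary objective in Parts A, A-2 and B, and the SAP plans no hypothesis testing (3.1.5), so the descriptive safety tables carry much of the report. A temporary hold and a permanent stop mean different things for tolerability. A hold is often the management step the protocol requires; a permanent stop means the patient could not go on with the drug. A single row covering both does not tell the reader which occurred.

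This matters for a known problem of this drug. Protocol 5.3.2 reports that Grade 2 infusion-related reactions were the most frequent related events in Part A, and that some patients stopped because reactions recurred despite premedication and slower infusion.

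The second issue is traceability. When an SAP leaves out a tabulation that its protocol promised, the section on changes should say so.

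**Working it through.** No arithmetic decides this point. The check compares what is collected, what is promised and what is planned.

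1. **How often a hold is expected.** Protocol 8.1.5.2 requires NM21-1480 to be withheld for any related event of Grade 2 or higher, apart from listed exceptions such as Grade 2 fatigue, alopecia, rash and laboratory abnormalities. Holds for moderate events are therefore routine and can fill the pooled row.

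2. **Whether term and grade can separate the outcomes.** For a Grade 2 infusion reaction, Table 8-1 (protocol 8.1.7) allows a same-day restart at half the rate if symptoms resolve within an hour. Otherwise, "dosing will be held until symptoms resolve and the participant should be pre-medicated for the next scheduled dose". It also says: "Participants who develop Grade 2 toxicity despite adequate premedication should be permanently discontinued from further IP administration". The hold and the permanent stop share one term and one grade, so tables by term and grade cannot tell them apart.

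3. **Whether another adverse event table catches the Grade 2 stop.** SAP 3.6.2 plans 8 tables by system organ class and preferred term and 2 more by highest grade, 10 in all. None is restricted to events that led to discontinuation. The Grade 3 or higher tables miss a Grade 2 event. The special-interest criterion for infusion reactions starts at Grade 3. The dose-limiting toxicity clause for any-grade events requiring removal (protocol 7.2.5.1) exempts infusion-related reactions.

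4. **What other SAP sections supply.** SAP 3.3.1 summarizes reasons for treatment discontinuation, and the groupings in 3.3 include each dose level, each cohort and the 800 mg total. SAP 3.3.8 summarizes interrupted or incomplete infusions with reasons, but specifies no summary of scheduled doses withheld because of an adverse event. SAP 3.6.2 lists all adverse event data by patient, and SAP 3.3.7 lists all concomitant medication.

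5. **What is left uncovered.** Two counts have no table: patients with a dose held because of an adverse event, and permanent stops caused by an event considered related to NM21-1480.

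6. **Protocol 10.6.6 against SAP 3.6.2.**

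| Promised tabulation | In SAP 3.6.2 | Named in SAP section 6 |
|---|---|---|
| Interruption or discontinuation | Yes, pooled | Not applicable |
| Dose reduction | No | No |
| Additional therapy | No | No |

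The last two rows differ in one respect. Additional therapy has its own recorded action in protocol 9.2.4.4. Dose reduction is not among the four action categories in 9.2.4.3, so it cannot be tabulated from that field.

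**The case against.** The strongest reply is that the pooling breaches nothing. Protocol 10.6.6 names reduction, interruption and discontinuation in one phrase. It asks for no separate rows, no drug-related version and no table by organ class and term, and protocol 10.1 lets the SAP modify methods. All of that stands. Nor is the row an outlier for lacking a drug-related version: the rows for special-interest events, immune-related events and deaths lack one too.

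The information is also largely recoverable. Disposition counts treatment stops by reason for each group. With 5 patients enrolled in each of A-2, B1 and B7 and 10 in B8 (SAP section 6), a reader can go through the cases one by one. This also stands, and it rules out a stronger reading that a reader might infer: that any share of the pooled row, from none to all, could be permanent stops. The disposition table gives stops by reason, so the documents do not leave that count open. A reader might also infer that a table of discontinuations by organ class and term is owed; the protocol does not require one.

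Two further replies carry less weight. The overview list is introduced as an inclusion list, and SAP section 7 puts detailed programming specifications in a separate document, so a split may exist there. That cannot be checked, and the SAP is where such a choice belongs. Section 6 does signal reduced outputs in general terms, but small numbers do not explain dropping a one-row summary when Part A alone exposed 26 patients (protocol 5.3.2).

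**Conclusion.** The point holds as a minor one. The adverse event overview cannot separate routine holds from treatment-ending toxicity. What is missing is a tabulated count of holds caused by adverse events and of the drug-related share of permanent stops. The number of stops by reason and the individual cases remain available elsewhere. This is a weakness in reporting, not a departure from the protocol.

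The departure is separate and smaller: the tabulations of events leading to additional therapy and to dose reduction, both promised in protocol 10.6.6, are absent from SAP 3.6.2 and not declared in section 6.

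The documents contain no counts of holds or stops, so the effect on reported tolerability cannot be sized. No primary estimate or decision rule changes. The conclusion assumes that the disposition reasons include adverse events, as the reasons listed in protocol 7.2.9 indicate, and that no unseen programming specification already makes the split.

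**What to change.** In SAP 3.6.2:

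- Replace the pooled overview row with two: TEAEs leading to permanent discontinuation, and TEAEs leading to temporary interruption. Give each overall and for NM21-1480-related events.
- Keep one listing and show the action-taken code in it.
- Add one overview row for TEAEs leading to additional therapy, taken from the other-action field.

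In SAP section 6, name every tabulation in protocol 10.6.6 that will not be produced. Dose reduction is the obvious candidate, since the action-taken field has no code for it.

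The count is 2 × 2 + 1 = 5 rows in place of 1, a net addition of 4. The protocol already has both action fields recorded, and SAP 3.1.7 already treats missing causality as related, so no new data are needed. The cost is a few sparse rows and some SAP wording.

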2.6 Study Endpoints – Part A

2.6.1 *Primary Endpoints*

- Incidence and nature of dose-limiting toxicities (DLTs)
- Incidence and severity of treatment-emergent adverse events (TEAEs) with specific focus on incidence and severity of immune-related adverse events (irAEs)

2.6.2 *Secondary Endpoints*

- PK parameters
 - AUC_{tau}
 - $AUC_{0-\text{inf}}$ (first dose only)
 - AUC_{0-t}
 - C_{max}
 - C_{min}
 - $t_{1/2}$
 - T_{max}
 - λ_z
 - CL
 - CL_{ss}

- V_d
- V_d_{ss}
- Frequency of specific anti-drug antibodies to NM21-1480

2.6.3 *Exploratory Endpoints*

- Best overall response (BOR)
- Objective response rate (ORR)
- Time-to-response (TTR)
- Duration of response (DOR)
- Progression-free survival (PFS)
- Overall survival (OS)
- Characterization of exposure-dependent PD markers of target and pathway engagement. Potential PD markers are summarized in detail in the below list of exploratory markers applicable to all Parts A, A-2 and B

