2.7 Study Endpoints – Part A-2

2.7.1 *Primary Endpoints*

- Incidence and severity of TEAEs with specific focus on incidence and severity of irAEs
- Characterization of exposure-dependent PD markers of target and pathway engagement. Potential PD markers are included in the below list of exploratory markers applicable to all Parts A, A-2, and B

2.7.2 *Secondary Endpoints*

- PK parameters
 - AUC_{tau}
 - AUC_{0-inf} (first dose only)
 - AUC_{0-t}
 - C_{max}
 - C_{min}
 - $t_{1/2}$
 - T_{max}
 - λz
 - CL
 - CL_{ss}
 - V_d
 - V_d_{ss}
- Frequency of specific anti-drug antibodies to NM21-1480

2.7.3 *Exploratory Endpoints*

- BOR
- ORR
- TTR
- DOR
- PFS
- OS

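### On-study irAE severity is a named focus of a primary endpoint in Parts A, A-2 and B, but no table specified in SAP 3.6.2 summarises irAEs by CTCAE grade

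*SAP*

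**What the plan says.** The Part A primary endpoint (SAP 2.6.1) is "Incidence and severity of treatment-emergent adverse events (TEAEs) with specific focus on incidence and severity of immune-related adverse events (irAEs"). For Part A-2 (SAP 2.7.1) it is "Incidence and severity of TEAEs with specific focus on incidence and severity of irAEs", and SAP 2.8.1 words the Part B endpoint the same way. The objectives table in protocol section 6 agrees.

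SAP 3.6.2 then specifies three groups of AE tables.

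- **Overview.** The TEAE row reads "Any TEAEs (overall, by maximum severity, and grade ≥ 3"). The row for drug-related TEAEs has the same split, and so does the AESI row: "Any TEAEs of special interest (overall, by maximum severity, and grade ≥ 3"). The irAE row reads only "Treatment-emergent irAEs".
- **Tables by SOC and PT.** TEAEs and related TEAEs each have an additional Grade ≥3 table. Treatment-emergent irAEs appear once, ungraded.
- **Tables by SOC, PT and grade.** These are introduced with "The number and percentage of patients with AEs will be summarized by SOC, PT, and highest CTCAE grade for the following types of AEs". Two types follow: TEAEs and related TEAEs.

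Beyond the tables, "Additional listings will present SAEs, AESIs, irAEs, TEAEs leading to temporary or permanent discontinuation of NM21-1480".

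The only irAE count by grade in the SAP is in section 3.3.5, and it covers irAEs during prior anti-cancer therapy. SAP section 6, on changes from the protocol, does not mention irAE severity.

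**The concern.** A primary endpoint with two stated components, incidence and severity, should have a planned summary of each. For irAEs the SAP plans only the first.

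Grade carries much of the clinical meaning here. Protocol Appendix VI makes continuing, withholding or stopping the drug depend on irAE grade for most event types. A bare irAE percentage counts a Grade 1 laboratory thyroid change and a Grade 3 hepatitis alike. If the SAP is followed as written, the study report will tabulate how many patients had an irAE, but not how many had a severe one, for any dose level, cohort or part.

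The gap weighs more in Part A-2. Its primary endpoints are AE incidence and severity, and pharmacodynamic markers. SAP 3.5.6 drops all pharmacodynamic analysis, so safety is the only primary endpoint of that part still analysed.

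**Working it through.** The plan gives no figure to reproduce. The check compares the endpoint with the table specifications, then asks whether another planned output fills the gap.

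**1. Severity breakdowns specified in SAP 3.6.2**

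| AE type | Overview, by severity | SOC/PT, Grade ≥3 version | SOC/PT by highest grade | Total |
|---|---|---|---|---|
| TEAEs | yes | yes | yes | 3 of 3 |
| Related TEAEs | yes | yes | yes | 3 of 3 |
| AESIs | yes | no | no | 1 of 3 |
| Treatment-emergent irAEs | no | no | no | 0 of 3 |

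**2. Can irAE grade be recovered from another table?**

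- *Graded TEAE tables.* Every treatment-emergent irAE is counted in them. But irAE status is an investigator flag in the eCRF, not a SOC or PT, so the irAEs cannot be picked out. For one preferred term, let *c* patients have the event, *a* of them flagged as irAE and *b* at Grade ≥3. With one record per patient, the number with a Grade ≥3 irAE can lie anywhere from max(0, *a* + *b* − *c*) to min(*a*, *b*). Terms also cannot be added up to a patient count, because one patient may contribute to several.
- *AESI rows.* One AESI criterion is "Any AE of CTCAE V5.0 Grade 3 or higher", whatever the cause. If investigators apply it, every Grade ≥3 TEAE is an AESI, so the Grade ≥3 AESI count equals the Grade ≥3 TEAE count and says nothing specific about irAEs. A Grade 1 or 2 irAE enters the AESI rows only through another criterion, such as the ALT/AST rise or a DLT.
- *DLT summary (SAP 3.6.1).* By protocol 7.2.5.1, DLTs are confined to the first 28 days and have listed exceptions. SAP 3.6.2 continues to collect late irAEs beyond 70 days after the last dose.
- *Listings.* These should show grade patient by patient, but they contain no counts.

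**3. Who is covered**

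- Part A: 26 exposed (protocol 5.3.2). Part A-2: 5. Part B: 5 + 5 + 10 = 20 (SAP section 6).
- Total: 26 + 5 + 20 = 51, assuming everyone enrolled in A-2 and Part B was treated.
- The 800 mg total required by SAP 3.1.1, by assigned dose: 9 evaluable in Part A (protocol Table 10-5) + 20 = 29. It is 30 if the one Part A patient who was exposed but not evaluable (26 − 25 = 1) was assigned 800 mg.

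**4. Are the data there?** Yes. SAP 3.6.2 has the investigator record irAE status in the eCRF, and protocol 9.2.4.1 requires a CTCAE v5.0 grade for every AE.

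**The case against.** The case for leaving the SAP alone has substance.

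- **Listings.** The irAE listing is planned, and with groups of 5, 5, 10 and 5 patients in B1, B7, B8 and A-2, counting severe irAEs by hand is easy. This stands, on the reasonable inference that the listing shows grade, since its columns are not specified. It limits the harm but does not supply a summary of a primary endpoint, least of all for the pooled 800 mg column.
- **The table list may not be closed.** The overview is introduced as including certain counts, and SAP section 7 leaves programming detail to a separate document. So further rows are not excluded. None is planned either, and the neighbouring rows show that a split is written out where one is intended.
- **Part A is already bounded.** Protocol 5.3.2 reports only two Grade 3 treatment-related events and none higher. On those data Part A has at most two Grade ≥3 irAEs, unless an event judged unrelated was flagged as immune-related. This stands for Part A as reported there; the documents give no such figure for A-2 or Part B.
- **The protocol does not require it.** Protocol 10.6.3 promises a separate irAE listing and summary without mentioning grade, and 10.6.6 asks for grade tables for AEs in general. This stands: the mismatch is between the SAP's own endpoint and its tables, not a breach of an explicit protocol table requirement.

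Two stronger readings are tempting. A reader might infer that every Grade 3 or higher irAE is a DLT, so that the DLT assessment suffers. Protocol 7.2.5.1 does not support that: the 28-day window applies, several Grade 3 immune-type events are excepted (for example, endocrinopathies controlled by hormone replacement), and DLTs have their own summary. A reader might also infer that the choice of 800 mg is undermined. The SMC and the sponsor settled on 800 mg as presumptive RP2D on 23 May 2022 from Part A data, and nothing in either document makes a dose decision depend on this table.

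**Conclusion.** The point holds as a gap in reporting. No table specified in SAP 3.6.2 summarises on-study irAEs by grade, although irAE severity is a named focus of a primary endpoint in Parts A, A-2 and B. The severity component therefore goes unsummarised for any part and for the 800 mg total.

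Its size is zero graded irAE summaries out of two irAE table specifications, over about 51 patients. That count describes scope, not an effect. No hypothesis test (SAP 3.1.5 plans none), stopping rule or dose decision is affected, and grade is not lost from the data. The conclusion rests on reading SAP 3.6.2 as written; the separate programming specifications could add the split but are not available here. The SAP should be changed, because its tables do not deliver its own endpoint and the repair is very small.

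**What to change.** In SAP 3.6.2, give the treatment-emergent irAE row of the overview the same three-way presentation as the rows for TEAEs, related TEAEs and AESIs: all grades, by maximum severity, and Grade 3 or higher. Present it in the groupings of SAP 3.1.1, including the 800 mg total.

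Adding treatment-emergent irAEs to the tables by SOC, PT and highest grade is optional; at these sample sizes most cells would be empty.

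The cost is a few extra lines in one existing table. It needs no new data and no change to any definition or analysis set.
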